## 2.1 STUDY RATIONALE

This project represents the first systematic investigation of the impact of the microbiome on nutritional status during pregnancy in young women and directly aligns with global health initiatives focused on this vulnerable cohort. Here our goal is to define the relationships between host nutritional status and microbiome dynamics during pregnancy and how they contribute to birth outcomes. The gut microbiome has a profound influence on host nutritional status. Dysbiosis (loss of diversity/beneficial microbes and gain of pathobionts) has emerged as a major factor in the development of undernutrition. Despite the importance of nutrition during pregnancy, few studies have examined the role of the microbiome on maternal health and birth outcomes. Further, little is known concerning the influence of enteric eukaryotic microbes, such as parasites, on the bacterial microbiome and host nutrition.

At the core of this study are two complementary cohorts of young women that provide an exceptional opportunity to obtain longitudinal samples to monitor the dynamic relationships between microbiome community structure and function with gut health and host nutritional status. This protocol will discuss the Pakistan cohort of the study, which builds off the partnership with Aga Khan University and [name] at SickKids. This cohort is expected to be exposed to a multitude of nutritional risks as well as pathogens and parasites associated with intestinal disease. To better define our target demographic, we focus on young mothers, 17-24 years of age, in the Matiari district of Pakistan, who are especially vulnerable to the impact of undernutrition[10]. A second complementary cohort will be based in Toronto, focused on refugee and young pregnant women in Toronto. This project will yield unprecedented insights into the relationships between prokaryotic and eukaryotic microbes in the gut and their associations with maternal health and birth outcomes.

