#### 2.2.4 EUKARYOTIC MICROBES ARE A KEY COMPONENT OF THE MICROBIOME

Typically, studies of the microbiome focus on bacterial components and tend to neglect the diverse array of eukaryotic microbiota. These include many considered to be parasites such as *Giardia*, *Cryptosporidium* and *Entamoeba*, each a significant global healthcare burden[51-54]. However not all parasitic infections cause disease; a study of Toronto daycares revealed a ~5% incidence of largely asymptomatic *Giardia* infections[55]. Thus, disease is a consequence of the complex interplay between the eukaryotic and bacterial microbiome and the host immune system[56, 57]. For example, *Prevotella copri*, is increased in patients with diarrheagenic *E. Histolytica* infections[54], while indole-producing bacteria such as *E. coli* CFT073 protect against *Cryptosporidium*[58]. Conversely, eukaryotic microbes may have neutral or even beneficial roles; *Blastocystis*, for example, has been associated with increased microbiome diversity[59, 60]. **While current knowledge of the interactions between bacteria and eukaryotic microbiota and their host is limited, recent advances, discussed below, provide the molecular tools required to dissect these interactions.**

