## 8.2 POTENTIAL PROBLEMS, MITIGATIONS AND EXPECTED RESULTS

We and others have already established the feasibility of obtaining DNA, proteomics and metabolomics datasets from LMIC settings (e.g.[4-6, 76, 108]). With the outstanding facilities available at AKU, we are therefore confident we will generate these datasets. In the unlikely event we find RNA yields are poor, we will revert to performing whole shotgun DNA sequencing (metagenomics), which also has the capacity to provide functional insights.

Our expectation is that: 1) study participants exhibiting positive maternal health and birth outcomes will be associated with more diverse communities than those exhibiting poor maternal health and/or birth outcomes; 2) pregnancies associated with poor nutritional status at the start of pregnancy, will exhibit a greater incidence of dysbiosis (e.g. loss of microbial diversity and decrease in otherwise dominant stool taxa e.g. Firmicutes and/or Bacteroidetes) throughout pregnancy; 3) pregnancies associated with pathogen exposure will result in dysbiosis; and 4) poor nutritional health will correlate with altered fecal metabolite profiles and changes in the expression of metabolic *pathway* enzymes encoded by the microbiome. Since analysis of microbiome data is a rapidly evolving field, to ensure data analysis is in line with best practices, we will adopt current state of the art bioinformatics tools for sequence processing, assembly, annotation and analysis. In case of delays or other issues that may be experienced at the Metabolomics Innovation Centre, we may rely on the SPARC Biocentre, hosted by the Hospital for Sick Children, to perform equivalent analyses.

As previous[39], we may expect specific taxa (prokaryotic or eukaryotic) will directly correlate

with nutritional status during pregnancy and birth outcomes. The core deliverables will be an unprecedented view of dynamic changes in microbial communities that contribute to nutritional status during pregnancy, together with the prediction of biochemical pathways and taxa responsible.

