##### **Clinical Variables**

1. Maternal BMI, MUAC and SFT (continuous variables)
2. Maternal gestational weight gain (continuous)
3. Maternal markers of inflammation (continuous)
4. Infant sex
5. Infant morbidity and mortality
6. Infant weight, height, head circumference (continuous)
7. Infant gestational age
8. Infant birth weight, Kg (continuous)
9. Breastfeeding duration (continuous)
10. Maternal age years
11. Maternal use of antibiotics
12. Infant use of antibiotics
13. Maternal calorie and macronutrient intake
14. Maternal incidence of pathobionts
15. Infant incidence of pathobionts

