##### **Microbiome Variables**

1. Maternal gut bacteria profile
2. Maternal eukaryotic microbe profile
3. Infant gut bacteria profile
4. Infant eukaryotic microbe profile
5. Maternal metabolomic profile of stool
6. Maternal metabolic pathway expression profile
7. Maternal bacterial gene expression profile

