#### 9.4.1 ADDRESSING THE PRIMARY OBJECTIVES

This study has two primary objectives: 1) To assess if alterations of the microbiota in the maternal gut (dysbiosis) are associated with maternal gestational weight gain; and 2) To determine the association between maternal microbiome dysbiosis during pregnancy and birth outcomes, infant growth, nutritional status and health status in the first year of life.

The first objective will be addressed through the following approaches. First, maternal gut bacteria and eukaryotic profiles will be used to calculate Bray-Curtis dissimilarity metrics between individual samples which will be leveraged in principal co-ordinate analyses to determine the extent samples collected at the first or third trimester, exhibiting similar gestational weight gains, co-cluster. Permutational multivariate analysis of variance (PERMANOVA) tests will assess the degree of overlap between samples exhibiting low gestational weight gain versus samples exhibiting high gestational weight gain. A lack of clustering in the first trimester, followed by clustering of samples on the basis of similar gestational weight gain would indicate that alterations in the maternal microbiota during the course of pregnancy, impacts gestational weight gain. Next, we will attempt to correlate changes in the alpha diversity (as measured by the Shannon and Simpson indices) of the gut microbiome samples between the first and third trimester, with gestational weight gain. A decrease in alpha diversity (indicative of dysbiosis) associated with low gestational weight gain, would again indicate that dysbiosis is associated with maternal weight gain. To examine the influence of individual taxa on gestational weight gain, we will perform bivariate analyses that examine the correlation (Pearson, Spearman) of each taxon with gestational weight gain. Correlations will examine taxon abundance in first and third trimester, in addition to the change in abundance between the two trimesters. The Benjamini-Hochberg procedure will be applied to correct p-values while controlling for false-discovery rates.

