#### 9.4.2 ADDRESSING THE SECONDARY OBJECTIVES

This study has the following secondary objectives: 1) To link the maternal microbiome to dietary intake, with a focus on calories and macronutrients; 2) To integrate maternal anthropometric factors, morbidity and mortality with microbiome data to reveal key modulators (microbial taxa and metabolites) of dietary intake during pregnancy and the post-partum period; 3) To determine the impact of the maternal microbiome during pregnancy, including the exposure to pathogens and parasites, on the development of the infant microbiome; and 4) To investigate the maternal microbiome's exposure to pathogens and parasites, and the association with intestinal inflammation.

To assess these secondary objectives, we will employ general linear models. In a first approach we will perform PERMANOVA and probe the association of microbial community structure with the clinical variables. Pair-wise differences in microbiome structure between patient samples at similar time-points are defined by abundance-weighted pair-wise differences using the Bray-Curtis dissimilarity metric. DESeq2, a method for differential analysis of count data, will subsequently be applied to investigate both associations of specific taxa with the clinical variables, together with the strength of those associations. DESeq2 will utilize default settings, and q-values calculated with the Benjamini-Hochberg procedure to correct p-values while controlling for false-discovery rates. These analyses will reveal which clinical variables (including exposure to pathogens and parasites) correlate with the maternal microbiome from a taxonomic perspective.

To probe the association of clinical variables with the function of the microbiome, PERMANOVA and DESeq2 analyses will be performed replacing microbial community structure metrics with microbial community function metrics, specifically: 1) metatranscriptomic profiles; and 2) stool metabolomic profiles. Profile differences will be defined through Spearman rank differences for metatranscriptomic data and Euclidean distance metrics for metabolomic profiles. These analyses will reveal microbial genes, metabolites and pathways that correlate with clinical variables.

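### Section 9.4.2 tests parasite or pathogen exposure against taxonomic profiles that may still contain the same organism; for parasites and the 18S profile the test is circular

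*Protocol*

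**What the plan says.** - **The test.** Protocol section 9.4.2: "In a first approach we will perform PERMANOVA and probe the association of microbial community structure with the clinical variables". Differences between women are measured by Bray-Curtis dissimilarity, and DESeq2 then tests individual taxa against the same clinical variables.
- **The conclusion to be drawn.** The same section says that this will show "which clinical variables (including exposure to pathogens and parasites) correlate with the maternal microbiome from a taxonomic perspective". Pathogen and parasite exposure is thus an explanatory variable.
- **The variables.** Table 8 (section 9.4) lists "Maternal incidence of pathobionts" among the clinical variables and "Maternal eukaryotic microbe profile" among the microbiome variables, next to the maternal bacterial profile. It does not say which assay supplies the first of these.
- **Where parasites are measured.** Section 2.2.4 says of the eukaryotic microbiota: "These include many considered to be parasites such as" Giardia, Cryptosporidium and Entamoeba. Section 8.1.2 profiles bacteria by 16S and eukaryotes by 18S, and introduces a TaqMan card covering 19 enteropathogens to define bacterial pathogen burden. In Table 4 of section 3, the endpoint for the objective on pathogen and parasite exposure names the same 16S and 18S surveys. No separate parasite assay is described.
- **Reuse.** Section 9.4.3 applies the framework of 9.4.2 to first-to-third-trimester differences in taxon abundance.

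**The concern.** If a woman counts as exposed because an organism is found in her stool, and the profile being compared includes that organism, exposed and unexposed women differ in at least that one component. PERMANOVA can then reject although nothing else in the gut differs. A DESeq2 test of that same taxon only recovers the grouping.

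Pathogen exposure is part of the central hypothesis in section 4.1. A significant 18S result would be reported as an association between parasite exposure and community structure, yet would not show whether the rest of the community differs, which is the question of interest.

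**Working it through.** **The plan's own figure.** The only power statement (section 9.1) is 80% power for r = 0.14 with 400 women at a type I error of 0.05. By Fisher's z, two-sided: atanh(0.14) × √397 − 1.960 = 0.1409 × 19.925 − 1.960 = 0.848, and Φ(0.848) = 80.2%. It reproduces, but it concerns alpha diversity and weight gain and has no bearing on this PERMANOVA.

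**Why the overlap produces a signal.** Let p be a profile without the organism. Give the organism share a and scale the rest down: the profile becomes ((1 − a)p, a). For profiles that sum to 1, Bray-Curtis is ½Σ|difference|. Between these two it is ½(a·Σp + a) = ½(a + a) = a. The organism alone therefore adds a dissimilarity equal to its share, always between exposed and unexposed women.

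**Inputs to the simulation.**
- From the protocol: 400 women (section 9.1) and about 50,000 reads per sample (section 8.1.2).
- Borrowed: the other protozoa in the 18S profile take prevalences from Table 3 (section 2.2.5), which describes malnourished children in Malawi. The focal organism is given 34% (Giardia and Blastocystis in that table), with 5% as a low case.
- Assumed: log-normal abundances; the organism's median share when present; four further eukaryotic taxa always present; a bacterial profile of 150 taxa.
- Null: exposure is drawn independently of every other taxon, so the true association with the rest of the community is zero.
- Test: pseudo-F = SS(group) / [SS(residual) / (n − 2)], 199 permutations, rejection at p ≤ 0.05, 60 to 100 runs per row.

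| Profile | Prevalence | Median share if present | Rejection, organism kept | Rejection, removed and rescaled |
|---|---|---|---|---|
| 18S | 34% | 1% | 96% | 5% |
| 18S | 34% | 2% | 100% | 7% |
| 18S | 34% | 5% | 100% | 5% |
| 18S | 34% | 10% | 100% | 5% |
| 18S | 34% | 20% | 100% | 3% |
| 18S | 5% | 2% | 35% | 5% |
| 18S | 5% | 5% | 91% | 7% |
| 16S | 34% | 0.05% | 8% | 3% |
| 16S | 34% | 0.1% | 10-13% (two sets of runs) | 5% |
| 16S | 34% | 0.2% | 36% | 5% |
| 16S | 34% | 0.5% | 92% | 5% |
| 16S | 34% | 1% | 100% | 3% |
| 16S | 34% | 3-10% | 100% | 3-7% |
| 16S | 5% | 0.1% | 5% | 5% |
| 16S | 5% | 1% | 34% | 4% |

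**Checks.** With the organism removed, mean R² was 0.0023-0.0027, against an expected null value of 1/(n − 1) = 1/399 = 0.0025. With it kept in the 18S profile at 34% prevalence, R² rose from 0.008 (share 1%) to 0.112 (share 20%). The Monte Carlo standard error of a 5% rate is √(0.05 × 0.95/100) = 2.2 points with 100 runs and 2.8 points with 60, so 3-7% agrees with the nominal 5%.

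**Parasite exposure against 16S.** The parasite is not in the bacterial profile, so this contrast corresponds to the 16S rows in the removed column: 3-7%. It is not circular.

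The trimester-difference profiles of section 9.4.3 were not simulated. The same reasoning applies wherever the exposure is defined by an organism whose change is part of the profile.

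**The case against.** **The main contrast is sound.** The protocol keeps 16S and 18S as separate surveys and separate Table 8 variables. Much of its interest is in how parasites relate to the bacterial community, and section 9.3 names pathogen presence against bacterial diversity. Section 9.4.2 also tests clinical variables against stool metabolites, which contain no taxon counts. This stands: a reader might infer that every microbiome association with pathogen exposure arises by construction, and the documents do not support that.

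**Bacterial pathogens have their own assay.** This stands in part. A separate assay does not remove the organism's reads from the 16S profile, but at a low share the effect is slight.

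**The objectives that name pathogens have other outcomes.** They concern the infant microbiome and intestinal inflammation, and the sentence at issue claims only correlation. This limits the importance. The sentence is nevertheless a stated output of the analysis, and for a parasite against 18S that correlation says nothing about the rest of the community.

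**Details may be left to a statistical analysis plan.** Variable derivation and filtering often are, and the source of the Table 8 pathobiont variable is not given. But the protocol itself fixes the test, the variables and the conclusion, and followed as written they give an uninformative result for this contrast.

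**Dysbiosis.** Section 2.1 has "Dysbiosis (loss of diversity/beneficial microbes and gain of pathobionts", and section 8.2 expects that "pregnancies associated with pathogen exposure will result in dysbiosis". A reader might infer that the expectation is true by definition. It is not: 2.1 joins loss of diversity or beneficial microbes with gain of pathobionts, so acquiring a pathogen does not suffice. Section 8.2 illustrates dysbiosis by loss of diversity and of dominant taxa, and section 9.4.1 works with "A decrease in alpha diversity (indicative of dysbiosis"). Nor does 9.4.2 use a dysbiosis variable, so the definition has no part in this PERMANOVA.

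**Conclusion.** The concern holds for profiles that contain the exposure-defining organism.

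- **Parasite exposure against 18S:** circular. False rejection is about 96-100% at 34% prevalence and 35-91% at 5%, against 3-7% with the organism removed. DESeq2 on that same taxon is circular too.
- **Bacterial pathogen against 16S:** depends on abundance. At 34% prevalence it runs from almost none (share 0.1% or less) to complete (1% or more); at 5% prevalence it is nil at a 0.1% share and 34% at a 1% share.
- **Parasite exposure against 16S:** unaffected.

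The sizes rest on assumed abundances and borrowed prevalences, since the protocol gives neither for this cohort. The direction does not: an organism kept in the profile adds its own share to the distance between the groups. The point should be corrected, but it concerns a secondary analysis and does not undermine the microbiome results as a whole.

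**What to change.** In section 9.4.2, and by reference in 9.4.3, state that when a pathogen or parasite is the exposure:

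1. the assay that defines the exposure is named;
2. the taxon that defines it, at the rank the survey resolves, is removed and the profile re-normalised before PERMANOVA;
3. that taxon is excluded from the DESeq2 results for that exposure.

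As an alternative for parasites, test exposure against the 16S profile only.

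The cost is one extra filtering step per exposure, with no new data. For 16S there is a real loss: removing a taxon at the rank resolved also removes its non-pathogenic reads. E. coli is an example, since section 2.2.3 names a pathogenic type and section 2.2.4 a protective strain.

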#### 9.4.3 ADDRESSING THE EXPLORATORY OBJECTIVES

This study has the following exploratory objectives: 1) To explore the role of the maternal gut microbiome during pregnancy and to identify gut community dynamics in pregnant women and how this impacts differences between dietary intake and nutritional status; 2) To investigate socio-economic factors; including gender, poverty, exclusion and empowerment, and their influence on the health of a mother's microbiome (assessed by alpha and/or beta diversity, and absence of pathogens); 3) To explore the role of the human microbiota on nutritional status by performing fecal microbiota transplants in germ free mice and sterile piglets.

For the first exploratory objective, we will apply the same statistical framework as we utilized for the secondary objectives here, however, we are concerned with changes in the microbiome within a patient from the first to third trimester. Consequently, microbiome structural and functional profiles will be generated from the difference in: 1) taxonomic abundances; 2) gene expression; and 3) metabolite concentrations, between the first and third trimesters. Profile differences will then be utilized in the PERMANOVA and DESeq2 approaches as described above to identify associations between clinical variables and changes in microbiome structure and function.

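### DESeq2 is planned for metabolite concentrations (9.4.2) and for within-woman differences (9.4.3), and Bray-Curtis carries over by reference to taxon differences; neither method is valid on that input

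*Protocol*

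**What the plan says.** Section 9.4.2 opens with "To assess these secondary objectives, we will employ general linear models". It makes this concrete as two procedures. PERMANOVA is run on taxonomic profiles with "abundance-weighted pair-wise differences using the Bray-Curtis dissimilarity metric". Feature-level tests use "DESeq2, a method for differential analysis of count data", with Benjamini-Hochberg q-values and the statement "DESeq2 will utilize default settings". For the function of the microbiome, "PERMANOVA and DESeq2 analyses will be performed replacing microbial community structure metrics with microbial community function metrics". The function metrics are the metatranscriptomic and the stool metabolomic profiles. For PERMANOVA they receive distances of their own: Spearman-based for expression and Euclidean for metabolites. Table 4 in section 3 describes the metabolomic output as concentrations.

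Section 9.4.3, exploratory objective 1, says "we will apply the same statistical framework as we utilized for the secondary objectives", but changes the input: "microbiome structural and functional profiles will be generated from the difference in: 1) taxonomic abundances; 2) gene expression; and 3) metabolite concentrations", taken between the first and third trimesters. It continues: "Profile differences will then be utilized in the PERMANOVA and DESeq2 approaches as described above". It names no distance, transformation or paired model of its own.

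**The concern.** DESeq2 fits a negative binomial model to counts. A concentration is not a count, so the metabolite step conflicts with the protocol's own description of the method. A difference between visits is not a count either, since it is negative for every feature that declines.

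Bray-Curtis divides by the summed abundances of the two profiles. It is a 0-to-1 dissimilarity only when all entries are non-negative. On signed changes the denominator can vanish or become negative.

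The analyses at stake are the false-discovery-controlled tests of single metabolites against the clinical variables (secondary objectives), and of change in single taxa, genes and metabolites against the same variables (exploratory objective 1). If the planned method cannot run, its replacement will be chosen after the data have been seen.

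**Working it through.** **Plan's own figure.** The only design figure is in section 9.1: 80% power for r above 0.14 with 400 women and alpha 0.05. It reproduces (power 0.80; smallest detectable r 0.1395) and plays no part in this point.

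**DESeq2.** Simulated data (60 women and 100 features, both assumed) were passed to DESeq2 1.42.0 in the forms that the protocol describes:

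| Input | Result |
|---|---|
| Raw counts, one visit | accepted |
| Count differences | rejected: negative values |
| Metabolite concentrations | rejected: non-integer values |
| Metabolite differences | rejected: negative values |

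Rounding concentrations to integers lets the software run, but the p-values then depend on the unit. A 1000-fold change of unit moved log10 p by a median of 0.22 and a maximum of 1.54, which is a factor of about 35 in p (10^1.54).

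**Bray-Curtis on taxon changes.** The index is BC(x, y) = Σ|x − y| / Σ(x + y).

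- For relative abundances or equal-depth counts, each woman's changes sum to 0. Any woman with a change therefore has at least one negative entry, and Σ(x + y) = 0 + 0 = 0 for every pair. With 400 women there are 400 × 399 / 2 = 79,800 pairs.
- Example in percentage points: x = (+10, −6, −4), y = (−3, +5, −2). The numerator is 13 + 11 + 2 = 26 and the denominator is 7 − 1 − 6 = 0, so the index is undefined.
- Some software uses Σ|x + y| as denominator. That gives 26 / (7 + 1 + 6) = 26/14 = 1.86, outside 0 to 1. Changing the sign of y swaps Σ|x − y| and Σ|x + y|, so the ratio r becomes 1/r. If changes are symmetric around 0, half of all pairs therefore exceed 1. Simulation (400 women, 50 or 200 taxa, 50,000 reads, assumed log-normal abundances) gave 50% with no shift, and 22–47% when a fifth of taxa shifted by 0.5–1.0 log units.
- Unequal depth does not rescue the index. With 35,000–65,000 reads per sample (60 women, 100 taxa, assumed), every pair of count-difference profiles fell outside 0 to 1, and 58% were negative. The raw counts gave 0.32 to 0.76.
- A separate simulated set run in vegan 2.7.1 produced a warning about negative entries. PERMANOVA returned a negative model sum of squares (F = −4.38, R² = −0.08).
- Euclidean distance on the example is well defined: √(169 + 121 + 4) = 17.1.

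**Amount of metabolite data.** Section 8.1.4 focuses metabolomics on 200 women at MV1 and MV2. That is 200 × 2 = 400 samples for 9.4.2 and 200 difference profiles for 9.4.3.

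**Conditional point on expression.** Section 8.1.3 normalises expression per kilobase and per million mapped reads (RPKM). With 30 million mapped reads, 100 reads on a 1 kb transcript give 100 / (1 × 30) = 3.33; at 0.5 kb the value is 6.67 and at 3 kb it is 1.11. DESeq2 also rejected simulated RPKM values. With raw read counts the metatranscript step in 9.4.2 is valid. The protocol does not say which is the input. The read count of 100, the transcript lengths and full mapping are assumptions.

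**The case against.** The strongest reply concerns Bray-Curtis. Section 9.4.3 names no distance. Section 9.4.2 sets Bray-Curtis for samples at similar time points and gives other data types other distances, and section 8.1.2 leaves room for further tools. The authors may therefore have meant to adapt the distance. This stands in part: the carry-over is by reference. But Bray-Curtis is the only taxon distance in the framework that 9.4.3 adopts, so that is how the text reads.

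Another denominator, Σ(|x| + |y|), gives 26/30 = 0.87 in the example and cannot exceed 1. That is correct, but it is a different index and the protocol does not specify it.

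DESeq2 stops with an error on such input, so a false result would not appear silently. This stands, and it limits the harm to an unplanned choice of replacement.

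The general linear models named in 9.4.2 and the simple tests in 9.3 can take continuous data. They can, but 9.4.2 expressly sends metabolomic profiles to DESeq2 and attaches its q-values there, while 9.3 states no false-discovery control for its tests. The commitment in 8.2 to current tools concerns sequence data and does not cover metabolites.

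Exact zero-handling values may fairly be left to a statistical analysis plan. The mismatch of method and input may not, because the protocol itself fixes both.

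**Conclusion.** The concern holds and should be fixed. DESeq2 on metabolite concentrations (9.4.2) and on within-woman differences (9.4.3) cannot run as written; this follows from explicit text and needs no assumption about the data. Bray-Curtis on taxon differences is invalid too, given that 9.4.3 imports it by reference. The zero denominator for all 79,800 pairs further assumes relative abundances or equal-depth counts, simple subtraction, and both stool samples from all 400 women. The simulated shares rest on assumed data. The expression point is conditional on RPKM being the input.

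No primary result is at risk. The analyses in 9.4.1, including the Benjamini-Hochberg-corrected correlations of taxon change with gestational weight gain, stand. So do the per-visit taxon analyses of 9.4.2, the Spearman and Euclidean PERMANOVAs, and the Wilcoxon, t-test, Spearman, Random Forest and network methods of 9.3.

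**What to change.** - Restrict DESeq2 to raw per-visit 16S/18S and metatranscript read counts, and state that RPKM values are not its input.
- Analyse metabolites as log concentrations under the general linear models already named in 9.4.2, with Benjamini-Hochberg control.
- For exploratory objective 1, fit linear models to MV2 − MV1 differences in log-ratio abundances (taxa, genes) and log concentrations (metabolites). For the sequence counts, an alternative is a paired per-visit count model with a visit-by-clinical-variable term. With a term per woman, the main effect of a variable fixed within woman is absorbed, but the interaction, which is the quantity of interest, remains estimable. Apply Benjamini-Hochberg control to either.
- For the PERMANOVA on taxon change, name a distance that allows negative values, such as Euclidean on log-ratio changes. Keep the Spearman and Euclidean PERMANOVAs for expression and metabolites.
- State a rule for zeros, for example adding 0.5 to each count and using half the lowest detected concentration, with one sensitivity value.

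The cost is rewording two paragraphs and stating the zero rule. Standard software suffices, and no new data or samples are needed.
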